8.8.1.1.2 Patient's Global Assessment of Disease Activity

The Patient's Global Assessment of Disease Activity will be recorded on a 0 to 100 visual analog scale (VAS), with 0 indicating "very well" and 100 indicating "very poor" to the question "Considering all the ways arthritis affects you, how well are you doing today?" (Appendix 13.3).

8.8.1.1.3 Physician's Global Assessment of Disease Activity

The Physician's Global Assessment of Disease Activity will be recorded on a 0 to 100 mm VAS, with 0 indicating "no disease activity" and 100 indicating "extreme disease activity". The evaluating physician and the subject must complete the global assessments independently of each other (Appendix 13.4).

8.8.1.1.4 Health Assessment Questionnaire – Disability Index (HAQ-DI)

The functional status of the subject will be assessed using the HAQ-DI. This 20-question instrument assesses the degree of difficulty a person has in accomplishing tasks in 8 domains (dressing, arising, eating, walking, hygiene, reaching, gripping and errands/chores). Responses are scored on a 4-point Likert scale from 0 indicating no difficulty to 3, indicating inability to perform a task in that area. The need for aids/devices or help from another person will also be recorded. The HAQ-DI total score ranges from 0 to 3 with higher scores indicating greater dysfunction (Appendix 13.5).

As part of the HAQ-DI, subjects will be asked to assess their average pain during the last week on a 0 to 100 mm VAS, with 0 indicating "no pain" and 100 indicating "severe pain". This assessment should be completed before the joint examination. This pain score will be used to derive the ACR20/50/70.

8.8.1.1.5 FACIT Fatigue Scale

The FACIT fatigue scale (version 4) measures an individual's level of fatigue during their usual daily activities over the past week. It consists of 13 questions with a 7-day recall period on a 5-point Likert scale, with 0 indicating "not at all" and 4 indicating "very much". The total score ranges from 0 to 52. The higher the score, the better the quality of life (Appendix 13.6).

8.8.1.1.6 36-Item Short-form Health Survey (SF-36)

The health-related quality of life of the subject will be assessed using the SF-36 (version 2) with a 4-week recall period. This consists of 36 questions belonging to 8 domains in 2 components:

- Physical well-being: 4 domains: physical functioning (10 items), role physical (4 items), bodily pain (2 items), and general health (GH) perceptions (5 items).
- Mental well-being: 4 domains: vitality (4 items), social functioning (2 items), role emotional (3 items), and mental health (5 items).

The remaining item (health transition) is not part of the above domains but is kept separately (Appendix 13.7).

These scales will be rescaled from 0 to 100 (converting the lowest possible score to 0 and the highest possible score to 100), with higher scores indicating a better quality of life.

8.8.1.2 Safety Assessments

8.8.1.2.1 Adverse Event Definitions and Reporting

8.8.1.2.1.1 Definitions

ICH, FDA and European guidance will be followed for AE reporting.

Adverse Event

An AE is any untoward medical occurrence in a clinical study subject administered a medicinal (investigational or non-investigational) product. An AE does not necessarily have a causal relationship with the treatment. An AE can therefore be any unfavorable and unintended sign (including an abnormal finding), symptom, or disease temporally associated with the use of a medicinal (investigational or non-investigational) product, whether or not related to that medicinal (investigational or non-investigational) product.

Serious Adverse Event

An SAE is any untoward medical occurrence that at any dose meets any of the following conditions:

- results in death.
- is life-threatening: the subject is at risk of death at the time of the event. It does not refer to an event that hypothetically might cause death if it were more severe.
- requires inpatient hospitalization or prolongation of existing hospitalization.
- results in persistent or significant disability/incapacity.

- is a congenital anomaly/birth defect.
- is a medically significant event that may not be immediately life-threatening or result in death or hospitalization but may jeopardize the subject or may require intervention to prevent one of the other outcomes listed in the definitions above.

Unexpected Adverse Event/Reference Safety Information

An AE is considered unexpected if the nature or intensity is not consistent with the applicable product reference safety information. For GLPG0634, the expectedness of AEs will be determined by whether or not it is an ADR listed in the IB.

Intensity of an Adverse Event

Each AE must be rated on a 3-point scale of increasing intensity:

- Mild: Transient or mild discomfort; no limitation in activity; no medical intervention/therapy required.
- Moderate: Mild to moderate limitation in activity; some assistance may be needed; no or minimal medical intervention/therapy required.
- Severe: Marked limitation in activity; some assistance usually required; medical intervention/therapy required; hospitalization possible.

If there is a change in intensity of an ongoing AE, it must be recorded as a separate event.

Causality Assessment

The following decision choice will be used by the investigator to describe the causality assessment between the reported event and the investigational medicinal product.

- Unrelated: No relationship between the AE and the administration of investigational product; related to other etiologies such as concomitant medications or subject's clinical state.
 - Unlikely: Event or laboratory test abnormality, with a time to study medication intake that makes a relationship improbable (but not impossible). Disease or other drugs provide plausible explanations.
 - Possible: Event or laboratory test abnormality, with reasonable time relationship to study medication intake which could also be explained by disease or other drugs. Information on drug withdrawal may be lacking or unclear.
 - Probable: Event or laboratory test abnormality, with reasonable time relationship to study medication intake. Event unlikely to be attributed to disease or other drugs. Response to withdrawal is clinically reasonable and rechallenge not required.
-

- Certain: Event or laboratory test abnormality, with plausible time relationship to study medication intake which cannot be explained by disease or other drugs. Response to withdrawal is plausible (pharmacologically, pathologically). Event definitive pharmacologically or phenomenologically (ie, an objective and specific medical disorder or a recognized pharmacological phenomenon). Rechallenge satisfactory, if necessary.

Action Taken Regarding Investigational Product

The action taken must be described by choosing among:

- Dose not changed: In case no action is taken regarding the study medication.
- Study medication permanently withdrawn: In case a subject is permanently withdrawn from the study.
- Study medication temporarily withdrawn: In case the study medication is temporarily withdrawn.
- Dose reduction: If a subject's daily dose is adjusted from 200 mg to 100 mg (q.d., once daily in the morning).
- Not applicable: Other situations (eg, in case an AE started after the last study medication administration).

Outcome

Each AE must be rated by choosing among:

- Recovered/Resolved.
- Recovered/Resolved with sequelae.
- Not recovered/Not resolved.
- Fatal.
- Recovering/Resolving.
- Unknown.

8.8.1.2.1.2 Recording Adverse Events

AEs will be recorded from the signature of ICF until the final Follow-up Visit. In case an AE is ongoing at that time, it will be followed up until resolution or until stabilization by the investigator's medical judgment.

It is the responsibility of the investigator to collect all AEs (both serious and non-serious) derived by spontaneous, unsolicited reports of subjects, by observation and by routine open questioning (such as “How do you feel?”).

Any adverse or unusual event occurring during or after the clinical study (until the last visit or the Follow-up Visit), whether observed by the investigator or investigational staff, or spontaneously reported by the subjects, will be recorded in the eCRF.

8.8.1.2.1.3 Managing Serious Adverse Events

Subjects experiencing an SAE or an emergency situation will be examined by a physician as soon as possible. The physician in attendance will do whatever is medically needed for the safety and well-being of the subject. The subject will remain under observation as long as medically indicated. Appropriate laboratory studies will be conducted until all parameters return to normal or are otherwise explained or stable. The subject will be followed until the SAE resolves or until the subject is medically stabilized.

8.8.1.2.1.4 Reporting Serious Adverse Events

All SAEs, whether or not deemed study medication-related, must be recorded in the eCRF and SAE form and reported by the investigator (Belgium) within 24 hours by facsimile. Other means of transmission can be decided where facsimile is not possible. The SAE form should include a clearly written narrative describing signs, symptoms, and treatment of the event, diagnostic procedures, as well as any relevant laboratory data and any sequelae.

Follow-up and outcomes should be reported for all subjects that experience an SAE. It is critical that the information provided on the SAE form matches the information recorded on the eCRF for the same event. In addition, the same information is to be recorded in the source documents.

Copies of additional laboratory tests, consultation reports, postmortem reports, hospital case reports, autopsy reports, and other documents should be sent when requested and applicable. Follow-up reports relative to the subject’s subsequent course must be submitted to [redacted] until the event has subsided or, in case of permanent impairment, until the condition stabilizes.

The contact information is:

[redacted]

8.8.1.2.1.5 Pregnancy

All initial reports of pregnancy in a subject and pregnancies in partners of male subjects included in the study must be reported to [redacted] by the investigator within

24 hours of knowledge of the event, using a pregnancy form. Any subject who becomes pregnant during the study must be promptly withdrawn from the study (not applicable if subjects are male). Spontaneous abortion is considered an SAE and will be reported as such.

The investigator will contact the subject at the expected time of delivery for follow-up on the pregnancy outcome. Abnormal pregnancy outcomes are considered SAEs and must be reported using the SAE Form.

8.8.1.2.1.6 Reporting Serious Adverse Events to Competent Authorities/ Ethics Committees

██████████ assumes responsibility for appropriate reporting of AEs to the regulatory authorities. ██████████ will also report to the investigator(s) all SAEs that are unlisted (unexpected) and associated with the use of the study medication. The investigator(s) (or ██████████ where required) must report these events to the appropriate IEC/IRB that approved the protocol unless otherwise required and documented by the IEC/IRB.

AE reporting, including suspected unexpected serious adverse reactions, will be carried out in accordance with applicable local regulations.

After termination of the clinical study (last subject last contact in the study), any unexpected safety issue that changes the risk benefit analysis and is likely to have an impact on the subjects who have participated in it, will be reported by the sponsor, ██████████ as soon as possible to the competent authority(ies) concerned together with proposed actions.

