8.7.1.1 Entry Visit (Extension Visit 1, Day -1)

The Entry Visit (Visit 1) will take place on Day -1 relative to the start of the study medication intake. There will be no gap between the core studies and the open-label extension study.

- Subjects will be assessed for eligibility against the inclusion and exclusion criteria.
- Entry Visit data will be those collected at the Week 24 visit from the previous core study in which the subject has participated (GLPG0634-CL-203 or GLPG0634-CL-204) for physical examination, 12-lead ECG, vital signs, clinical laboratory tests (including serum pregnancy test), SJC66, TJC68, Physician's Global Assessment, Patient's Global Assessment, health assessment questionnaire – disability index (HAQ-DI), FACIT fatigue scale, and SF-36 questionnaire. Data on demographics, baseline characteristics, and medical history will be retrieved from the

Screening visit of the previous core studies. Data will not be re-entered in the GLPG0634-CL-205 eCRF but will be retrieved from the preceding core study database during statistical programming.

- Urine (dipstick) pregnancy test for females of childbearing potential.
- Tuberculosis (TB) blood test (QuantiFERON-TB gold test^a) will be performed.
- Any new AEs that have occurred since signing the informed consent form (ICF) will be documented.
- Any ongoing or unresolved AEs and concomitant medications from the preceding core study will be documented on the GLPG0634-CL-205 AE and concomitant medication pages of the eCRF, respectively.
- IXRS call.

^a In case of a positive or confirmed indeterminate result for QuantiFERON-TB gold test: 1.) Permanent withdrawal of the subject from the study; 2.) Consultation with the local infectious disease specialist is highly recommended to investigate if the patient has active or latent TB or no TB

When all the Entry Visit procedures have been performed and the investigator has confirmed the subject's eligibility for the study, the study medication will be dispensed to the subject. The subject will start taking the study medication on Day 1 and subsequent visits will be scheduled.

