8.9.1.3 Safety Variables

Clinical safety will be evaluated by assessing treatment-emergent AEs (TEAEs), physical examinations, laboratory assessments, ECG results, and vital signs results. The safety analysis may combine the data of all 3 studies (GLPG0634-CL-203, GLPG0634-CL-204, and GLPG0634-CL-205).

A treatment-emergent analysis of AEs will be done, based on the start date of the AE. TEAE (AE and SAE) preferred terms, intensity, frequency, relationship to study medication, dose reductions, and temporary/permanent treatment stops will all be tabulated. An additional analysis based on patient-years of exposure may be added when deemed useful.

Original results and changes from baseline will be summarized for all laboratory, vital signs, and ECG parameters, intended to detect any changes in safety parameters that could be attributed to GLPG0634 dosing. No imputations will be done for safety data in cases where subjects discontinued the study prematurely.

Further subgroup analyses (e.g., a selection of TEAEs with an onset date during the first weeks or months, or a division according to the mean actual dose) and exploratory analyses may be added when deemed appropriate.

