7.1.5. Treatment-Emergent Adverse Events

7.1.5.1. Definition of Treatment-Emergent Adverse Events

Treatment-emergent adverse events (TEAEs) are defined as any AEs with an onset date on or after the filgotinib start date in the core studies or GLPG0634-CL-205, and no later than 30 days after permanent discontinuation of filgotinib in GLPG0634-CL-205.

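### An adverse event that began before filgotinib and eases on filgotinib can be tabulated as treatment-emergent, because intensity changes open a new record and the SAP looks only at onset date

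*Protocol*

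**What the plan says.** Four provisions act together.

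- **Recording.** Under the intensity scale in Protocol 8.8.1.2.1.1: "If there is a change in intensity of an ongoing AE, it must be recorded as a separate event". No direction of change is given.
- **Carry-over.** Protocol 8.7.1.1 brings events across from the core study at entry: "Any ongoing or unresolved AEs and concomitant medications from the preceding core study will be documented on the GLPG0634-CL-205 AE and concomitant medication pages". Within 205, "AEs will be recorded from the signature of ICF until the final Follow-up Visit", so events can also be on record before the first dose.
- **Treatment emergence, protocol.** Section 8.9.1.3: "A treatment-emergent analysis of AEs will be done, based on the start date of the AE".
- **Treatment emergence, SAP.** Section 7.1.5.1 covers "any AEs with an onset date on or after the filgotinib start date in the core studies or GLPG0634-CL-205". The window closes 30 days after filgotinib is stopped for good.

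Neither document links the parts of a split event or compares intensity before and after the first filgotinib dose. For laboratory data the SAP does make such a comparison: 7.2.2.1 requires a rise of at least one toxicity grade from filgotinib baseline, and 7.2.3.2 counts worsening from that baseline.

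**The concern.** A treatment-emergent event should be one that is new or worse on treatment. Here the recording rule gives an ongoing event a fresh record when it gets better, and the emergence rule sees only that record's date. Recovery can therefore appear in the filgotinib tables as harm. The primary objective is long-term safety and tolerability, and TEAE tables are one of its main outputs, alongside examinations, laboratory tests, ECGs and vital signs. Through this route the misclassification can only add to filgotinib counts.

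**Working it through.** The plan gives no figure on this point, so there is none to reproduce. The check has two parts.

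**1. Apply the rules to every possible change.** Take an event that began before filgotinib and changes intensity afterwards, with the separate record dated at the change.

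| Change | TEAE under current text | Enters moderate-or-higher table | TEAE if worsening were required |
|---|---|---|---|
| mild to moderate | yes | yes | yes |
| mild to severe | yes | yes | yes |
| moderate to severe | yes | yes | yes |
| moderate to mild | yes | no | no |
| severe to mild | yes | no | no |
| severe to moderate | yes | yes | no |

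All six become TEAEs, and three of the six are improvements. Counting each subject once per summary (SAP 7.1.6.1) prevents double counting. It does not remove a subject whose only on-filgotinib record for a preferred term is the improved one.

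**2. Size where the rule is directly confirmed.** Study 203 placebo responders stayed on placebo to Week 24 and took their first filgotinib in 205 (table in Protocol 8.1; Protocol 8.6.4).

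- Number of such subjects: not stated. Protocol Table 6-1 gives 38 of 86 placebo subjects with ACR20 at Week 12. The responder definition in Protocol 8.1 needs only the joint-count part, so it is looser. Assumed range: 38 to 60.
- Share with a placebo-period TEAE: 51.2% (Protocol 6.4, all placebo-exposed subjects in study 203).
- Roll-over: the group sizes in Tables 6-1 and 6-2 sum to 594 + 283 = 877, and 739/877 = 0.843. Assumed equal across arms.
- With a placebo-period event and in 205: 38 × 0.512 × 0.843 = 16.4, and 60 × 0.512 × 0.843 = 25.9.
- Ongoing at the switch and later changing intensity: assumed 20 to 40% ongoing and 30 to 60% of those changing, so 0.2 × 0.3 = 0.06 to 0.4 × 0.6 = 0.24. This gives 16.4 × 0.06 = 1.0 to 25.9 × 0.24 = 6.2 subjects.
- Half of the changes are improvements (assumed): 0.5 to 3.1 subjects. As a share of 739: 0.07% to 0.42%, or about 0.1 to 0.4%.

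**Moderate-or-higher table.** Only severe-to-moderate changes matter. Severe TEAEs occurred in 1.2% of 86 and 1.4% of 72 placebo-exposed subjects (Protocol 6.4), about one in each study, before requiring that the event was ongoing and then eased on filgotinib.

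**Treatment-related tables.** Under SAP 7.1.3 the record enters only if the investigator marks causality as possible, probable or certain, or leaves it blank.

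**The case against.** The strongest reply is that a step is unseen. Neither document says that the separate record's onset is the date of the change, and the outcome category for a recovering event (Protocol 8.8.1.2.1.1) lets a site show improvement without a new record. This stands as a qualification. It does not remove the point: the recording rule is mandatory and silent on direction. If sites instead keep the original onset date, a genuine worsening on filgotinib would fail the onset-date test. The convention needs stating either way.

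It is also fair that the study is open-label and descriptive with no formal testing, that over-reporting harm is the conservative direction, that all events are listed with a treatment-emergence flag, and that the overall proportion with any TEAE would barely move. All of this limits the consequence.

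A reader might infer a larger effect by counting every placebo subject: 86 + 72 = 158 of 877, about 44 + 28 = 72 with a placebo-period TEAE, about 61 after roll-over, and with the factors 0.06 to 0.24 some 4 to 15 subjects. The documents do not support that figure. It counts worsening, which is properly treatment-emergent. It also applies the 205 recording rule to all study 204 placebo subjects and to study 203 placebo nonresponders, who started filgotinib at Week 12 within core studies whose protocols are not supplied. For them the 205 rule applies only to a placebo-period event still ongoing at 205 entry.

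**Conclusion.** The definition gives a wrong classification for improving events, on the natural reading of onset date, and nothing else in the protocol or SAP prevents it. It also departs from the principle that the SAP applies to laboratory abnormalities.

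The effect is small and mainly on preferred-term incidence: about 0.5 to 3 subjects (0.1 to 0.4% of 739) in the group where the rule is directly confirmed. That range rests on the assumed 38 to 60 subjects, equal roll-over across arms, 6 to 24% of placebo-period events ongoing and changing, and half of the changes being improvements. Events from before the first filgotinib dose in other subjects, still ongoing at 205 entry, add a number that the documents do not allow one to estimate. A material distortion of the moderate-or-higher or treatment-related tables might be inferred but is not supported. This is a minor correction, worth making because it is cheap.

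**What to change.** Add to SAP 7.1.5.1 that a record continuing an event of the same preferred term already present before the first filgotinib dose is treatment-emergent only if its intensity is higher than the last intensity before that dose. Define a continuation as a record of the same preferred term that starts on, or the day after, the end date of the previous record. Confirm in the eCRF completion rules that the separate record's onset is the date of the change, and state that convention in the SAP.

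The cost is one SAP sentence and one derivation step on data already collected. The downside is that linking by preferred term and dates needs a short data check, since coding differences or date gaps could break a link. If the SAP is already final, SAP section 1 requires the change to be documented in the CSR.

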8.8.1.2.2 Clinical Laboratory Evaluation

The hematology and clinical chemistry laboratory analyses will be performed at a central laboratory ██████████. Reference ranges will be supplied by the central laboratory and used by the investigator to assess the laboratory data for clinical significance and pathological changes.

The total amount of blood to be taken at the AV will not exceed 43 mL.

The total amount of blood to be taken at Entry Visit, QEV, Final Visit/EDV and Follow-up Visit will not exceed 39 mL.

The following laboratory safety tests will be performed at every visit:

Hematology

Hemoglobin, hematocrit, WBC count (total and differential), RBC count, differential lymphocyte count (by flow cytometry: CD3, CD19, CD4, CD8, CD3-/CD16+, and CD56+), platelet count, activated partial thromboplastin time, and prothrombin time.

Clinical Chemistry

Creatinine, blood urea nitrogen, aspartate aminotransferase, ALT, gamma-glutamyltransferase, alkaline phosphatase, total bilirubin, amylase, lipase, albumin, total protein, sodium, potassium, chloride, glucose, uric acid, total cholesterol, HDL- and LDL-cholesterol, triglycerides, calcium, and phosphorus.

Serum CRP will be measured at every visit except the Follow-up Visit.

Serum pregnancy test for females of childbearing potential is performed at the AV, Final Visit/EDV and the Follow-up Visit.

Hormone tests (for male subjects only)

Testosterone (total and free), LH, FSH, PRL, and inhibin B.

Urinalysis

pH, glucose, ketone bodies, indicators of blood and WBC, and protein (quantitative).

Urine pregnancy test for females of childbearing potential is performed at Entry Visit and QEV, and also performed every 4 weeks during the dosing period through 35 days after their last dose of study drug using home pregnancy tests that will be provided to them. Refer to Appendix 13.8 for details.

Other

TB blood (QuantiFERON-TB Gold) test at Entry Visit and AV.

